trends in GH, IL-6, and IGF-1 over the 6 week rehabilitation protocol. Patients will receive the blood draws in clinic at the following time points: prior to 1st day of rehabilitation, half-way through the protocol (approximately 3 weeks), and after completing rehabilitation (approximately 6 weeks). ELISA will be used to quantify GH, IL-6, and IGF-1 plasma levels at the 6 time points. The trends in these 3 blood markers will be compared between the two groups.

Methods and Measures

Design

Describe the basic design of the study, use as many of the following terms as apply.

- *For intervention studies: randomized controlled trial; placebo-controlled; before-after trial; pilot study*

Setting

Academic medical center

Subjects selection criteria

• Inclusion Criteria

- Inclusion criteria will be any injured patient ages 18 to 55 years with clinical and magnetic resonance imaging (MRI) consistent with a formal diagnosis of non-operative rotator cuff and/or biceps tendinopathy, no prior upper extremity ipsilateral procedures or history of deep vein thrombosis, and those willing to be part of the study.

• Exclusion Criteria

- Exclusion criteria includes patients younger than 18 or older than 55 years of age, a history of revision surgery or prior ipsilateral upper extremity surgery, concomitant ligamentous, tendinous, or cartilage injury that would alter postoperative rehabilitation protocol, inability to comply with the proposed follow-up clinic visits, and patients lacking decisional capacity.

• Sample Size

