- Based on the literature review, there are no published studies that have evaluated the effect BFR therapy on shoulder injury rehabilitation. Some studies have taken a pilot study approach and used 12 patients in each limb based off what has been recommended in the previous literature.^{45, 46} However, others evaluating the effect of BFR therapy on quadriceps strength after ACL reconstruction have evaluated their sample size based on their own preliminary pilot studies and established sample sizes of 24 per group in order to achieve 80% power.⁴⁷ A previous study comparing GH levels between healthy individuals undergoing BFR strength training vs those without was used to estimate the number of patients needed to achieve at least 80% power.⁴⁸ Based on the difference in GH between the two groups, an effect size of 2.203 was calculated. An *a priori* power analysis demonstrated that 6 patients were required in each group in order to achieve a power of 90%. However, we feel that the standard deviation of the current study may be larger, and as such, for this pilot study we will recruit a minimum of 8 patients in each arm. However, we hope to recruit at least 12 in each arm by the time the study is completed in order to have 24 patients similar to established sample sizes in other BFR studies.⁴⁷

Interventions and Interactions

Study Arms

Once consented, patient will be enrolled in of the two study arms prior to beginning physical rehabilitation. Patients will be randomized to one of the study arms using Microsoft Excel (version

Protocol version:

Template updated 9.24.14

16.82). Prior to beginning therapy, patients will undergo a blood draw at the clinic to establish baseline blood biomarkers. The patient will also undergo upper extremity physical strength assessment, and functional evaluation prior to beginning therapy. Baseline patient reported functional status will also be evaluated through upper extremity-specific questionnaires. During physical therapy, participants will undergo blood draws, receive electronic questionnaires, and undergo assessment of biomechanical at specified time points outlined below. Patient questionnaire information will be de-identified and coded into an encrypted centralized database. The schematic in **figure 1** provides the time points of each datapoint collected.

[figure not shown]

Figure 1. Schematic of study workflow indicating timepoints for carrying out study aims

BFR Protocol

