Subject descriptive statistics will be analyzed using mean \pm standard deviation for continuous variables, and frequencies and percentages for categorical variables. Normality analyses will be performed utilizing data visual inspection and parametric testing. Averages between the two groups will be compared using independent T-test and chi-square analysis were appropriate. Repeated measures ANOVA will be performed to evaluate statistical significance in blood biomarkers.

Human Subjects Protection

Subject Recruitment Methods

Describe how and where subjects will be identified and recruited. Indicate who will do the recruiting, and tell how subjects will be contacted. Describe efforts to ensure equal access to participation among women and minorities. Describe how you will protect the privacy of potential subjects during recruitment.

- For studies using recruitment flyers and advertisements, please provide copies of these materials for IRB review.
- For studies using PHI to identify subjects via medical records search or referral from a treating physician, who will then be contacted, you will need a limited waiver of HIPAA authorization, If this applies to your study, please provide the following information:
 - Under this limited waiver, you are allowed to access and use only the minimum amount of PHI necessary to review eligibility criteria and contact potential subjects. What information are you planning to collect for this purpose?
 - How will confidentiality/privacy be protected prior to ascertaining desire to participate?
 - When and how will you destroy the contact information if an individual declines participation?

Protocol version:

Template updated 9.24.14

Informed Consent

Signed informed consent will be obtained from each subject. Informed consent will be gathered by the one of the study coordinators or study investigators in clinic after being screened with inclusion/exclusion criteria and prior to undergoing non-surgical treatment for the injury.

Confidentiality and Privacy

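### The repeated measures ANOVA planned for the biomarkers names no tested term and no rule for incomplete patients; its conventional complete-case form could use up the margin that 8 per arm keeps for a larger SD.

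*Combined protocol and SAP*

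**What the plan says.** The Analytical Plan gives the biomarkers one sentence: "Repeated measures ANOVA will be performed to evaluate statistical significance in blood biomarkers". It does not say whether the group effect or the group-by-time interaction is the test, how baseline enters, whether a sphericity correction applies, or what happens to a patient with a missing draw.

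Aim 2 (Objectives) states the question: "The trends in these 3 blood markers will be compared between the two groups".

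The Blood Biomarkers section schedules three draws: before therapy, half-way, and on completion. Aim 2 lists the same three but then refers to 6 time points for the assays. The only protection against data loss is replicate assay of each sample, which cannot replace a draw that was never taken.

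The Sample Size section uses a GH comparison to "estimate the number of patients needed to achieve at least 80% power". From that source "an effect size of 2.203 was calculated", and "6 patients were required in each group in order to achieve a power of 90" per cent. It then says "we feel that the standard deviation of the current study may be larger", so "we will recruit a minimum of 8 patients in each arm", and adds that "we hope to recruit at least 12 in each arm by the time the study is completed". No dropout or missed-draw allowance appears.

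**The concern.** Repeated measures ANOVA, as usually run, needs a complete row for each patient, so one missed draw removes all of that patient's data. With 8 per arm, three incomplete patients in one arm leave 5. The two patients added above 6 were added for variability, and deletion would draw on the same two. If missed draws are related to recovery, a complete-case comparison can also be biased.

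The second gap is the unnamed test. The group main effect averages over all visits, including baseline, where randomised arms have no expected difference. The group-by-time test does not. With three markers and neither term named, the choice stays open until the results are known.

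**Working it through.** **Inputs from the documents.** d = 2.203; 6 per group for 90% power; goal of at least 80%; minimum 8 per arm, hoped-for 12; three draws.

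**Assumptions.** Two-sided alpha 0.05 and 1:1 allocation (neither stated); missed-draw rate q = 5, 10 or 15% per draw, independent (no rate given); within-patient correlation r = 0.3 to 0.7 with equal variances and equal correlations across visits.

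**1. The plan's own figure.** Two-sample t-test, noncentrality d√(n/2), 2n − 2 degrees of freedom:

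| n per arm | Power at d = 2.203 |
|---|---|
| 5 | 86.1% |
| 6 | 92.9% |
| 8 | 98.3% |
| 12 | 99.9% |

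The smallest n reaching 90% is 6, so the stated number reproduces. It is a single-time-point comparison with no allowance for loss.

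**2. Complete cases from 8 per arm.** Expected number = 8(1 − q)^k, with k = 3 draws at risk, or k = 2 if baseline is always obtained. The chance that either arm falls below 6 is 1 − P², where P is the binomial probability of 6 or more complete out of 8.

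| q | Expected, k = 3 | Either arm below 6 | Expected, k = 2 | Either arm below 6 |
|---|---|---|---|---|
| 5% | 8 × 0.857 = 6.9 | 18% | 8 × 0.9025 = 7.2 | 7% |
| 10% | 8 × 0.729 = 5.8 | 61% | 8 × 0.81 = 6.5 | 33% |
| 15% | 8 × 0.614 = 4.9 | 88% | 8 × 0.7225 = 5.8 | 63% |

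At 12 per arm with k = 3, the chance is 0.1, 4 and 25%. If there really were 6 time points, 5% missed at 8 per arm would give 59%.

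**3. What the loss costs.** The smallest d with 80% power is about 1.51 at 8 per arm and about 2.02 at 5 per arm. In terms of the standard deviation:
- 8 per arm tolerates 2.203/1.51 = 1.46, an SD about 46% larger than planned.
- 5 per arm tolerates 2.203/2.02 = 1.09, about 9% larger.

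**4. Which term is tested.** Suppose there is no baseline difference and an effect d at both later draws. The mean over three visits then has difference (2/3)d and standard deviation √((1 + 2r)/3), so the standardised effect is (2/3)(2.203)/√((1 + 2r)/3):
- r = 0.3: 1.469/0.730 = 2.01
- r = 0.7: 1.469/0.894 = 1.64

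| n per arm | Group main effect, r = 0.3 to 0.7 | Group-by-time, r = 0.3 to 0.7 |
|---|---|---|
| 8 | 96 to 86% | 96 to over 99% |
| 6 | 88 to 73% | 88 to over 99% |
| 5 | 80 to 63% | 80 to 99% |

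The two tests have about equal power at r = 0.3; the main effect falls behind as r rises.

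**5. What the replacement recovers.** At q = 10% and 8 per arm:
- Baseline as covariate needs baseline plus at least one later draw: 0.9 × (1 − 0.1²) = 0.891, so 7.1 usable of 8, and a 9% chance that either arm falls below 6.
- Constrained baseline needs at least one later draw: 1 − 0.1² = 0.99, so 7.9 of 8, and a chance of about 0.01%.

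**6. Precision from baseline adjustment.** Against a single-visit change from baseline, the variance ratio is (1 − r²)/(2(1 − r)) = (1 + r)/2. That is 0.75 at r = 0.5 (a 25% cut) and 0.85 at r = 0.7 (a 15% cut).

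**The case against.** A reader might infer that the plan will delete patients, dilute the effect with baseline, and so fall below its own required number. The documents do not support that chain.

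- Deletion is the usual behaviour of the method; the Analytical Plan is silent on it.
- Averaging in baseline happens only if the group main effect is tested, and Aim 2's reference to trends points to group-by-time. Averaging could in any case lower power but never the patient count.
- The 6 is the figure for 90% power, while the stated aim is at least 80%, which 5 per arm meets at d = 2.203.

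The loss model can also be called pessimistic. The baseline draw is a step before therapy starts. Later draws are taken on therapy days, with two sessions a week, which leaves room to reschedule. Patients unable to attend follow-up are excluded. If baseline is always obtained, the expected number at 10% missed stays above 6. If whole patients leave instead, losses clump: 20% incomplete at 8 per arm gives a 36% chance that either arm falls below 6, and a mixed model recovers little from a patient lost before any later draw. At the hoped-for 12 per arm the risk is small unless about 15% of draws or more are missed.

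All of this stands and limits the size of the point. It does not supply the missing rule, the missing allowance or the named test, and 8 is the committed minimum.

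**Conclusion.** The concern holds in a limited form: a method that conventionally needs complete data, no rule for incomplete patients, no attrition allowance, and no named test. At 8 per arm, 5 to 15% missed draws would leave an expected 6.9 to 4.9 complete patients per arm, or 7.2 to 5.8 with baseline always obtained. Falling to 5 would not by itself miss the 80% goal at the planned effect size. It would cut the tolerable increase in standard deviation from about 46% to about 9%, and a larger standard deviation is the reason the plan gives for recruiting 8. The dilution from baseline is conditional on a main-effect test that Aim 2 does not suggest.

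The sizes rest on the assumed missed-draw rates, their independence, the assumed alpha and the assumed correlations. The gaps in the text do not. This should be changed; it does not invalidate the design.

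**What to change.** In the Analytical Plan, replace repeated measures ANOVA with a linear mixed model for each marker:

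- Use all available draws, with arm-by-visit terms, an unstructured covariance (so sphericity is not needed) and Kenward-Roger degrees of freedom.
- Constrain baseline to be equal between arms. Baseline as a covariate is an acceptable alternative, but it drops patients without a baseline draw.
- Name one prespecified post-baseline between-arm contrast per marker that matches the trends hypothesis in Aim 2.
- Choose the analysis scale from the normality checks already planned.
- State the missing-data assumption, and add an allowance for incomplete patients to the Sample Size section.
- Reconcile the three scheduled draws with the 6 time points in Aim 2.

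The change of model uses data already planned and needs no extra visits or assays. Its cost is slightly more complex reporting. An allowance for incomplete patients would raise recruitment only if it took the target above the numbers already stated.

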Patients assigned to the BFR group will undergo BFR therapy during each session throughout the entire rehabilitation protocol. The standard rehabilitation protocol recommended by the physical therapists at WFBH is 2 sessions a week for 6 weeks. The therapy will be performed by one of the WFBH physical therapists who is trained and certified in using BFR therapy. The standard BFR protocol that is implemented by the Wake Forest physical therapists and recommended by expert opinion involve performing 4 separate exercises during each session. Each exercise will be done 4 consecutive times, starting with 30 repetitions, followed by 15 repetitions performed 3 times. Each set will be separated by 30 seconds break. After the finishing the 4 sets for one specific exercise, the patient will rest for 2 minutes prior to beginning the next 4 sets. In summary, the patient will perform 4 sets of 4 different exercises, perming the following repetitions: 30-15-15-15.

In the BFR group, the tourniquet will be pressurized to 50% limb occlusion pressure (LOP), which is the pressure necessary for occluding 50% of arterial limb flow in the upper extremity. The amount of cuff inflation is personalized to each patient as a safety measure and for maximizing the acute physiological response.⁴⁰ In the sham BFR group, the tourniquet will be pressurized to 0% occlusion pressure, while maintaining enough pressure to keep the tourniquet in place.

Protocol version:

Template updated 9.24.14

The tourniquet system (Delfi, Medial Innovations Inc) used in our physical rehabilitation clinic allows a patient specific LOP to be measured and automatically calculates the patient's personalized tourniquet pressure (PTP) as percentage of LOP. As an additional safety measure, the cuff automatically shuts off after 8 minutes to prevent prolonged restriction, and is locked from turning back on for 2 minutes. The sets for each exercise are structured so that the patient is able to finish 4 sets of one specific exercise within the 8 minute time limit.

Shoulder Strength and Cross Sectional Area Measurement

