Blood samples will be acquired at baseline prior to intervention and at specific time points throughout the rehabilitation process to evaluate the effect of BFR therapy on the recovery of muscle, tendon, and ligamentous damage. Samples will be collected prior to beginning physical therapy, half-way through the structured protocol, and once the patient has completed rehabilitation. These blood samples will be collected by a member of the research team, who is trained in phlebotomy and is someone other than the principal investigator, and stored in a locked freezer until all samples for all patients have been collected. The patients will receive the blood draws in the physical therapy clinic on the day of their rehabilitation appointment. Once completed, GH, IGF-1, and IL-6 will be quantified using ELISA assays performed in the Wake Forest orthopedic surgery department. Each sample will have 3 technical duplicates analyzed to avoid loss of data during sample processing.

Patient Functional Status

Protocol version:

Template updated 9.24.14

Shoulder/Elbow functional status will be assessed using the following questionnaires that have been previously vetted for evaluation after upper extremity surgery: *Quick Disabilities of the Arm, Shoulder, and Hand (DASH)* survey, American Shoulder and Elbow Surgeons (ASES) standardized assessment form, visual analog scale for pain and satisfaction, and return to sport/daily activity questionnaires.^{42, 43} Patient reported outcomes will be captured prospectively over the course of one year using the PatientIQ, a web-based data collection healthcare platform. A blinded de-identified email and/or text message will be sent at baseline, and once cleared by therapy, as well as 6 and 12 months after completing therapy. After three days, if a participant does not respond to the survey, a second email and/or text message will be sent. If the participant does not respond after three consecutive weeks, a phone call will be administered to encourage continued participation.⁴⁴

Outcome Measure(s)

- *Shoulder strength, and rotator cuff muscle cross sectional area,*
- *Blood markers: GH, IGF-1, and IL-6*
- *Patient reported outcome measures: DASH, ASES, visual analog scale for pain and satisfaction*

Analytical Plan

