There are potential risks in this study. Risks and side effects related to this study. Patients may experience discomfort, bruising and/or bleeding where the needle is inserted. Occasionally some people become dizzy lightheaded or feel faint. Infection may occur on rare occasions. Risks of blood flow restriction tourniquet includes development of a blood clot, which could result in breathing complications if the clot travels to the lung. These risks have been minimized by excluding patients with risk factors for blood clots, as well as ensuring that the cuff is inflated to standard measurements that limit this risk. Other risks for tourniquet use include pain and discomfort at the site. However, the standard protocol limits the compression of the tourniquet to 30 second intervals, and there are no reports of persistent pain after sessions. The benefit of BFR therapy in shoulder injury is unknown. It is possible that by being in the BFR rehabilitation group, rehabilitation process may be slower than undergoing rehabilitation with BFR included.

References

1. Steinberg L: *Baseball Has A Serious Injury Problem*. Available at: <https://www.forbes.com/sites/leighsteinberg/2018/07/24/baseball-the-most-dangerous-sport-in-america/>. Accessed November 2, 2018.
4. Mascarenhas R, Verma NN: Editorial Commentary: Muscle Atrophy After Arthroscopic Rotator Cuff Repair-Reversible? *Arthroscopy* 2016;32:2488-2489.

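### The written plan names cuff-site pain and clot as tourniquet risks but specifies no systematic, by-arm collection or summary of either

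*Combined protocol and SAP*

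**What the plan says.** The risk paragraph under Reporting of Unanticipated Problems, Adverse Events or Deviations attaches two harms to the cuff. One is clot: "Risks of blood flow restriction tourniquet includes development of a blood clot". The other is local: "Other risks for tourniquet use include pain and discomfort at the site". The same paragraph adds that lasting pain after sessions has not been reported.

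Under BFR Protocol, the rehabilitation schedule "is 2 sessions a week for 6 weeks". The comparator is a sham cuff at 0% occlusion pressure.

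Outcome Measure(s) lists strength and muscle cross-sectional area, three blood markers, and "Patient reported outcome measures: DASH, ASES, visual analog scale for pain and satisfaction". It has no adverse-event or tolerability outcome. Under Patient Functional Status, the surveys "will be sent at baseline, and once cleared by therapy, as well as 6 and 12 months after completing therapy". The Analytical Plan names descriptive statistics, t-tests, chi-square tests and repeated measures ANOVA for biomarkers. It names no safety summary.

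Data and Safety Monitoring gives the principal investigator, helped by study staff, responsibility for monitoring safety. The reporting section requires prompt reporting of unanticipated problems, events that are serious and unexpected, deviations and protocol changes.

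**The concern.** The sample-size section calls this a pilot and says that no published study has examined this therapy in shoulder injury rehabilitation. The risk paragraph says that its benefit there is unknown. How well patients tolerate the cuff is basic information from such a study, and a randomised sham cuff is a natural comparator for it.

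If nobody asks about cuff pain in a fixed way, the trial will hold only what patients happen to mention. A report with few complaints could then reflect lack of collection rather than good tolerability. The statement about lasting pain could not be checked in this population. Session-level pain also cannot be recovered reliably after therapy ends.

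**Working it through.** **Step 1. Which risks belong to the cuff.** The risk paragraph ties clot and site pain or discomfort to the tourniquet. Bruising and bleeding belong to the blood draw: "Patients may experience discomfort, bruising and/or bleeding where the needle is inserted". Dizziness and infection follow in the same run of text. Both arms have the same blood draws. The point therefore concerns clot and cuff-site pain only.

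**Step 2. What each planned contact records.**

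| Contact | Recorded, per the text | Cuff tolerability or adverse-event item |
|---|---|---|
| Baseline | Strength, ultrasound, blood, questionnaires | None stated |
| 12 therapy sessions | Nothing routine beyond the half-way measures | None stated |
| Half-way | Blood draw, strength | None stated |
| End of therapy or clearance | Strength, ultrasound, blood, questionnaires | None stated |
| 6 and 12 months after therapy | Questionnaires | None stated |

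Study Arms says that electronic questionnaires are received during therapy, at time points outlined later. The time points written later give none between baseline and clearance, and the listed questionnaires contain no safety item. Figure 1, which is said to show the timing of each data point, is not visible.

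**Step 3. Whether other provisions fill the gap.**
- Cuff pain is already named as a risk and is usually not serious, so a duty worded around unanticipated problems and serious, unexpected events does not clearly reach it. Clot is also a named risk. Reporting an event is in any case different from asking the same question in both arms.
- The pain scale is listed among the measures of shoulder and elbow function. It does not ask about the cuff site.
- Confidentiality and Privacy limits collection to what the study outcomes need. With safety absent from the outcomes, the text gives no basis for recording tolerability.

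**Step 4. Size of the gap.**
- Sessions per patient: 2 per week × 6 weeks = 12.
- Patient-sessions over both arms: 12 × 16 = 192 at the minimum of 8 per arm; 12 × 24 = 288 at the hoped-for 12 per arm. These are repeated observations on 16 or 24 people.
- Clearance survey to 6-month survey: about 26 weeks, if clearance coincides with the end of therapy.

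**Step 5. What collection could show.** The plan gives no harm rate or safety sample size to reproduce. Its one sample-size figure, 6 per group for growth hormone at effect size 2.203, does reproduce: with two-sided alpha 0.05 (assumed; none is stated), the noncentral t distribution gives 86.1% power at 5 and 92.9% at 6. It has no bearing on harms.

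For harms, each patient counts once and no dropout is assumed.
- One-sided 95% upper bound after zero events, 1 − 0.05^(1/n): 31.2% at n = 8; 22.1% at n = 12. The two-sided exact interval, 1 − 0.025^(1/n), reaches 36.9% and 26.5%.
- Chance of at least one event in an arm, 1 − (1 − p)^n, over assumed rates:

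| Assumed rate p | n = 8 | n = 12 |
|---|---|---|
| 1% | 7.7% | 11.4% |
| 5% | 33.7% | 46.0% |
| 10% | 57.0% | 71.8% |
| 20% | 83.2% | 93.1% |

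- Fisher's exact test, two-sided, needs at least 5 events against 0 to fall below 0.05: p = 0.026 at 8 per arm and 0.037 at 12 per arm.

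A common complaint such as cuff discomfort would probably be seen. A rare one such as clot could not be compared between arms.

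**Step 6. A related inconsistency.** The risk paragraph reassures the reader that compression is limited to 30-second intervals. BFR Protocol describes 30-second breaks between sets and a cuff that shuts off automatically after 8 minutes. These passages must be reconciled. The length of compression is part of the basis for expecting little pain.

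**The case against.** The strongest reply is that safety is not ignored. The principal investigator has a stated monitoring duty and serious, unexpected events must be reported. Pain is rated in both arms at four time points, and a research-team member meets the patient in the therapy clinic half-way and at completion. Both aims concern function and biomarkers. With 8 to 12 per arm, no useful comparison of clot is possible in any case.

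Much of this stands, and it rules out several stronger readings that a reader might infer:
- **That the trial yields no harm data, or that reporting is optional.** The reporting duty and the four pain ratings contradict this.
- **That bruising, bleeding and infection are uncollected cuff harms.** The risk paragraph places them with the blood draw.
- **That exactly none of the 12 sessions has a planned record.** The written schedule shows none, but the general mention of questionnaires during therapy and the unseen Figure 1 leave modest doubt.
- **That an unbiased comparison of harm is thrown away.** The numbers support description only. The therapist probably knows the arm, which is an inference because the plan does not describe therapist blinding. Items that the therapist records could therefore still be affected.

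The reply does not supply a fixed question about cuff pain, a place to record it, or a table by arm.

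**Conclusion.** The point holds in a limited form. For the two risks that the protocol itself ties to the cuff, the written plan contains no systematic, by-arm collection or summary during the 12 sessions or between the clearance and 6-month surveys. The main loss is a description of common cuff discomfort in 16 to 24 patients; a comparison of clot risk was never within reach.

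The conclusion assumes that Figure 1 adds no safety item beyond the text and that the questionnaires mentioned during therapy are those listed under Patient Functional Status. It is an improvement that should be made, because it serves patient safety and costs little. It does not affect the efficacy or biomarker analyses.

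**What to change.** 1. **At each session, in both arms,** complete one short fixed form: the patient's own 0–10 rating of cuff-site pain, any pain persisting since the last session, arm swelling or breathlessness, and early cuff release (yes/no). Cuff pain should be rated by the patient, because the therapist may know the arm.
2. **In the existing PatientIQ surveys,** add one adverse-event item. One extra message soon after the last session is optional.
3. **In Outcome Measure(s) and the Analytical Plan,** list cuff-related adverse events and early cuff release as a descriptive safety outcome. Tabulate them per patient by arm with exact confidence intervals, and state that the sample cannot compare clot risk.
4. **Reconcile** the two descriptions of compression time in the risk paragraph and BFR Protocol.

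The cost is about a minute of form-filling per session, roughly 12 minutes per patient over the programme (12 × 1), using staff and a platform already in place. Therapist knowledge of the arm may still colour the items that the therapist records, and the report should say so.

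### Two safeguards in the risk paragraph, a 30-second compression limit and exclusion of clot risk factors, do not match the BFR Protocol and the eligibility criteria

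*Combined protocol and SAP*

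**What the plan says.** **Compression time.** The risk paragraph, which closes the section Reporting of Unanticipated Problems, Adverse Events or Deviations, states: "Other risks for tourniquet use include pain and discomfort at the site". It then offers two reassurances: "the standard protocol limits the compression of the tourniquet to 30 second intervals", and "there are no reports of persistent pain after sessions".

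The standard protocol is set out under BFR Protocol. Each exercise is done in four sets, "starting with 30 repetitions, followed by 15 repetitions performed 3 times". On rests it says: "Each set will be separated by 30 seconds break". On cuff time it says that "the cuff automatically shuts off after 8 minutes to prevent prolonged restriction", after which the cuff is locked for 2 minutes, and that the sets are arranged so that "the patient is able to finish 4 sets of one specific exercise within the 8 minute time limit".

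**Clot risk.** The risk paragraph names a blood clot that could reach the lung as a hazard of the tourniquet and says: "These risks have been minimized by excluding patients with risk factors for blood clots". It adds that cuff pressure is kept to standard values. Under Subjects selection criteria, the one clot-related item is the absence of prior deep vein thrombosis, placed in the inclusion list. The exclusion list covers age, revision or prior ipsilateral surgery, concomitant injury, inability to attend follow-up, and lack of decisional capacity.

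**The concern.** The risk paragraph attributes a compression limit to the standard protocol, but the section describing that protocol does not contain it. The 30 seconds found there is a rest time, and the cuff-time limit found there is measured in minutes. A reader, or the IRB, cannot tell what compression time the pain mitigation refers to.

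The clot statement raises a similar but softer problem. On its plain reading, excluding patients with clot risk factors is broader than excluding those with one particular event in their history. The Informed Consent section says patients are screened against the listed criteria, so staff following those criteria could enrol people whom the risk paragraph appears to say are kept out.

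What is at stake is the accuracy of the safety description on which the study was submitted. The trial's estimates and tests are not touched.

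**Working it through.** **Inputs, all from BFR Protocol**

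- Repetitions per exercise: 30 + 3 × 15 = 75.
- Rests within an exercise: 3 × 30 s = 90 s.
- Automatic shut-off: 8 × 60 = 480 s.
- Repetition tempo: not given. Call it *t* seconds; the values below are assumptions.
- Cuff condition during the rests: not given. Both possibilities are tested.

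**Can the 30-second figure be reproduced?** There is no stated figure from which to derive it. The shut-off is 480 / 30 = 16 times as long. The limit therefore has to be tested against the structure of the session.

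**Reading A: cuff inflated through the rests.** Inflation per exercise = 75*t* + 90 s. The 90 s of rests already exceeds 30 s, so the limit fails at any tempo. The 8-minute limit is met for *t* up to (480 − 90) / 75 = 5.2 s per repetition. The shut-off is thus compatible with a wide range of tempos and does not imply 30-second compression.

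**Reading B: cuff released at each rest.** Inflation per set = 30*t* for the first set and 15*t* for each of the other three. The first set takes 30 s at *t* = 30/30 = 1 s; a later set takes 30 s at *t* = 30/15 = 2 s.

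| Assumed tempo (s per repetition) | Reading A: whole exercise | Reading B: first set | Reading B: each later set | Reading B: sets within 30 s |
|---|---|---|---|---|
| 1 | 165 s | 30 s | 15 s | 4 of 4 |
| 2 | 240 s (4.0 min) | 60 s | 30 s | 3 of 4 |
| 3 | 315 s | 90 s | 45 s | 0 of 4 |
| 4 | 390 s (6.5 min) | 120 s | 60 s | 0 of 4 |
| 5 | 465 s | 150 s | 75 s | 0 of 4 |

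On Reading B, the four sets all comply at 1 s or faster, three comply above 1 s and up to 2 s, and none complies above 2 s. The section neither describes release at the rests nor sets a tempo that would secure compliance, and it describes no cycling of the cuff within a set.

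**Clot screening, side by side.** No arithmetic applies beyond a count. Clot-related criteria: one in the inclusion list (prior deep vein thrombosis) and none among the five exclusion items. That one criterion is a clot risk factor, so the safeguard is partly met. No listed criterion covers any other clot risk factor. The pressure safeguard does have a counterpart in BFR Protocol, where inflation is individualised, and it is not in dispute.

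**The case against.** The strongest reply on compression is that a device ceiling of 8 minutes does not contradict a shorter working limit. With the cuff released at rests and a tempo of 1 s or faster, every set would stay within 30 s. The wording may also be a garbled reference to the 30-second rests, which would make it a drafting slip. It is fair that the text shows an unsupported figure and a silence, not a measured compression time, and that the minute-by-minute values rest on an assumed tempo. But the mismatch does not need those values: nothing stated in BFR Protocol yields a 30-second limit under either cuff condition. If the figure is a rest time reported as a compression limit, then the stated safeguard is wrong as written.

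On clots, the reply is that the risk paragraph does not define its term and may loosely summarise the thrombosis criterion, and that a negative inclusion criterion excludes as effectively as an exclusion item. Both points stand. Where the criterion sits is unimportant; what remains is a difference of breadth, which is why this part is secondary.

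It is also true that treatment would be delivered according to BFR Protocol, by a certified therapist with automatic shut-off, and that the consent form is not available here, so no effect on what participants were told can be shown.

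**Conclusion.** The concern holds. With high confidence, the risk paragraph claims a compression limit that the operative section does not contain. The contrast is 30 s of claimed compression against a 30 s rest and a 480 s shut-off covering 75 repetitions and 90 s of rests. This conclusion needs no assumption about tempo or cuff condition; only the durations in the table do.

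With less confidence, the clot safeguard is overstated: one specific criterion stands behind a claim about risk factors in general. That rests on the plain reading of an undefined term.

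This should be fixed, because the statements are safety assurances to the IRB, but it has no bearing on outcomes, sample size or analysis.

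**What to change.** Reconcile BFR Protocol with the risk paragraph so that a single description of compression duration appears in both, including whether the cuff is inflated during the rests between sets. Reconcile the eligibility criteria with the risk paragraph so that the clot screen applied and the clot safeguard claimed are the same. Then check that the consent form listed in the Appendix agrees with both. The investigators and the IRB should decide which text is correct in each case; this review takes no view on that.

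The cost is a wording amendment through the IRB. Depending on how the clot statement and the criteria are aligned, a few candidates might become ineligible; the document gives no figure from which to estimate how many.
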